2.8.3 Abnormally low anthropometric values

Abnormally low anthropometric outcomes were:

- a. Percentage of children who are wasted, i.e. with weight-for-length z-score less than -2 (i.e WLZ < -2) at 3, 6, 12 and 18 months of age.
- b. Percentage of children severely wasted, i.e. with weight-for-length z-score less than -3 (WLZ < -3) at 3, 6, 12 and 18 months of age.

2.9 Analysis principles

- The primary analysis will be by intention-to-treat. That is, results for all women enrolled (including data on their infants) will be analyzed according to the group to which they were assigned regardless of any protocol violations. Data on subjects who were lost to follow-up because of death, travel from the study site, or refusal to continue with the study will be included in the analysis if available.
- All tests will be two-sided, at 5% level of significance.
- Where more than 10% of observations are missing for a dependent variable, we will report the number of observations used in the analysis.

3.0 Design

3.1 Sample size and power

Sample size calculations were based on being able to detect an effect size of 0.3 (difference between groups, divided by the pooled SD) for each outcome, assuming 3 groups, power of 80% and alpha=0.05. This required 216 per group, for a total of 648 subjects. Allowing for up to 25% loss to follow-up by 18 months, we needed to recruit 864 subjects. For the biochemical outcomes, we assumed an effect size of at least 0.5, which required a subsample of 79 per group, for a total of 315 subjects after allowing for attrition.

3.2 Informed consent issues

All eligible women did sign or thumbprint informed consent for their own participation and for the participation of their babies (upon delivery) prior to being enrolled. If a participant or their parent (in the case of infants) withdraws consent (refuse to continue in the study) at any point of the study, then we will stop any study treatment or follow-up, and if the participant is a pregnant woman, we will advise her to obtain routine supplements from the antenatal clinic. Data on participants who refuse to continue in the study will be included in our analysis on the intention-to-treat basis. However, the primary outcome data for such participants, if missing, will not be imputed.

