4.9 Comparison of primary outcomes at birth and 18 months of age

The ANCOVA to determine the effects of the intervention on birth length (crude length and length-for-age z-score) and length-for-age z-score at 18 mo among the three intervention groups will be performed using PROC GLM. Results will be summarized as mean and SD and tabulated, by group (**Table 2** and **Table 3**).

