4.10 Comparison of secondary outcomes

i. Comparison at single time points

Comparison of secondary outcomes at single time points will be performed using PROC GLM (for continuous outcome variables), and PROC FREQ and PROC LOGISTIC for categorical outcome variables. Continuous variables will be summarized using either mean and SD, or median and range. Categorical variables will be summarized using percentages and Odds Ratios, with 95% Confidence Intervals (95% CI).

Analysis of several secondary outcomes at birth and 18 months of age will be presented alongside the primary outcomes in **Table 2** and **Table 3** as well as in **Table 4**. Prior to the analysis of additional secondary outcomes at other single time points, this SAP will be updated to include those specific single time points, and how results will be presented.

ii. Comparison of repeated measures

For continuous outcome variables, a linear mixed model (PROC MIXED) will be used to compare patterns in the outcome variables across time among the groups. For categorical variables, a variant mixed model logistic regression (SAS PROC GLIMMIX) will be used. Prior to analysis of repeated measures, this SAP will be updated to include the specific analyses and the presentation of the results.

4.11 Selection of covariates and effect modifiers in the analysis of primary outcomesBelow we list the two primary outcomes to be analyzed (both at single time points), and indicate the covariates and effect modifiers that will be used for each analysis. Each of the effect modifiers will be considered separately in the regression model to avoid collinearity.

Primary	Analysis	Covariates	Effect modifiers
outcome			
variable			
Birth length	ANCOVA	- Maternal height	- Maternal height
(crude	(SAS Proc	- Maternal BMI	- Maternal BMI
length in cm	glm)	- Gestational age at enrolment	- Gestational age at enrollment
and length-		- Maternal age	- Maternal age
for-age z-		- Child sex	- Child sex
score)		- Maternal education	- Maternal education
		- Proxy for SES	- Proxy for SES
		- Parity	- Parity
		- Season at enrolment	- Season at enrolment
		- Mother's marital status	- Maternal anemia at enrollment
Length-for-	ANCOVA	- Maternal height	- Maternal height
age z-score	(SAS Proc	- Maternal BMI	- Maternal BMI
at 18 months	glm)	- Gestational age at enrolment	- Gestational age at enrollment
		- Maternal age	- Maternal age
		- Child sex	- Child sex
		- Maternal education	- Maternal education
		- Proxy for SES	- Proxy for SES

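### The primary 18-month LAZ analysis uses only children with an observed 18-month length, leaves earlier lengths unused, and has no sensitivity analysis for missing data

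*SAP*

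**What the plan says.** - **Population.** Section 2.9: "The primary analysis will be by intention-to-treat", defined as analysis of all enrolled women and their infants by assigned group. For people lost through death, travel or refusal it adds a condition; the sentence ends "refusal to continue with the study will be included in the analysis if available".
- **Model.** Section 4.9: the ANCOVA for birth length and 18-month LAZ "among the three intervention groups will be performed using PROC GLM". The lead-in to section 4.11 treats both primary outcomes as single-time-point outcomes. The covariates listed there are maternal and household characteristics, season and child sex. Under section 4.8 each is kept only if associated with the outcome at the 10% level. No earlier child length is on the list.
- **Expected loss.** Section 3.1: "Allowing for up to 25% loss to follow-up by 18 months, we needed to recruit 864 subjects".
- **Missing outcomes.** Section 3.2, on participants who refuse to continue: "the primary outcome data for such participants, if missing, will not be imputed". Section 2.9: "Where more than 10% of observations are missing for a dependent variable, we will report the number of observations used in the analysis". The only sensitivity analysis in the SAP (section 4.3) concerns outliers in secondary outcomes.
- **Data at hand.** Sections 2.7.2 and 4.7 schedule child length at birth, 3, 6, 12 and 18 months. For repeated continuous measures, section 4.10(ii) says "a linear mixed model (PROC MIXED) will be used to compare patterns in the outcome variables across time among the groups", but this sits under secondary outcomes.

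**The concern.** PROC GLM deletes any record without an outcome value. With loss at the planned ceiling, a quarter of those enrolled would contribute nothing to one of the two primary analyses. The result is then unbiased only if, within group and given the retained covariates, lost children would have had the same 18-month LAZ as those measured. The SAP neither states that assumption nor tests it.

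The assumption could fail differently by arm. Blinding is only partial, and only LNS-arm infants receive a supplement (section 2.1), so families' reasons for staying or leaving may differ between arms. A child's earlier lengths are the most direct information on whether those lost were growing differently, and the primary model does not use them. Tables 1a and 1b describe only participants who completed the study, so they would not show how the lost differed from the retained.

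**Working it through.** **1. The plan's own figures.** Inputs from section 3.1: three groups, effect size 0.3 SD, alpha 0.05, power 80%, 25% loss. Take a one-way ANOVA with extreme groups 0.3 SD apart and the third midway, noncentrality n × 0.3² / 2, and df 2 and 3n − 3. At n = 216 power is 80.2%, and this is the smallest n reaching 80%. Then 3 × 216 = 648 and 648 / 0.75 = 864. Both stated figures reproduce. Per group, 864 / 3 = 288 are enrolled. At 25% loss 288 − 216 = 72 per group (216 in total) have no 18-month LAZ.

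**2. Possible bias.** Let m be the share lost in an arm and g the mean of retained minus lost children in that arm, in SD units and after covariate adjustment. The retained mean exceeds the full-arm mean by m × g. The bias of a two-arm contrast is m₁g₁ − m₂g₂, which at 25% loss in both arms is 0.25 × (g₁ − g₂). The SAP gives no values for g, so the gaps below are assumptions.

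| Gap g₁ − g₂ (SD) | Bias (SD) | Share of 0.3 SD |
|---|---|---|
| 0 | 0 | 0% |
| 0.2 | 0.05 | 17% |
| 0.4 | 0.10 | 33% |
| 0.6 | 0.15 | 50% |

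Unequal loss rates also matter. If g = 0.3 in both arms, loss of 20% against 30% gives (0.30 − 0.20) × 0.3 = 0.03 SD. If rates and gaps are the same in both arms, the bias is zero.

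**3. Simulation.** Two arms of 288, true difference 0.30 SD, about 25% loss per arm. In one arm only, the log-odds of loss rise by 0.5 or 1.0 per SD of shorter earlier length. Every child has that earlier length, which favours the alternative method.

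| Correlation, earlier with 18-month | Complete-case estimate | Estimate using earlier length |
|---|---|---|
| 0.5 | 0.24 to 0.19 | 0.30 |
| 0.7 | 0.22 to 0.14 | 0.30 |
| 0.85 | 0.20 to 0.11 | 0.30 |

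With loss unrelated to earlier length, both methods return 0.30.

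**4. Precision.** Assume 288 per group, loss that is permanent once it occurs, and correlation 0.95 × b^(months apart) with b from 0.95 to 0.98. The 12-to-18-month correlation is then 0.70 to 0.84 and birth-to-18-month 0.38 to 0.66. Sum over loss patterns (children in the pattern) × (inverse correlation matrix of their observed visits), invert, and take effective n = 1 / variance of the 18-month mean.

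| Retention at 0/3/6/12/18 months | b | Effective n | Power at 0.3 SD |
|---|---|---|---|
| 0.90/0.85/0.82/0.79/0.75 | 0.95 | 226.7 | 82.2% |
| same | 0.98 | 238.2 | 84.1% |
| 0.95/0.92/0.88/0.82/0.75 | 0.95 | 232.0 | 83.1% |
| same | 0.98 | 247.0 | 85.5% |

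The complete-case comparison is 216 and 80.2%.

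**5. Who can be helped.** In the first schedule 10 of every 25 lost children (40%) have no length at all and 4 of 25 (16%) have a 12-month value. In the second the figures are 5 of 25 (20%) and 7 of 25 (28%).

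**The case against.** The other side has a fair case, and it limits the point in several ways.

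- **The label.** A reader might infer that the SAP promises intention-to-treat and then breaks the promise. It does not: section 2.9 defines the term by assigned group and openly includes lost subjects only where data exist. The label is loose, not contradicted.
- **Imputation.** A reader might take section 3.2 as a general ban. It covers only those who refuse to continue. For travel, death or missed visits the SAP has no rule either way, and deletion follows from the procedure chosen.
- **Bias.** Nothing in the SAP shows that loss depends on growth, or does so differently by arm. The 25% is an upper allowance, not a forecast.
- **Power.** There is no shortfall: 864 already covers the allowance. The gain from earlier lengths is modest and rests on assumed inputs.
- **Earlier lengths.** The documents do not show that most lost children have a recent length. Enrolment is at or before 20 weeks' gestation, so losses may precede birth.
- **Reporting.** Tables 2 and 3 already give n per arm, and section 4.1 plans a CONSORT flow diagram.
- **The remedy.** A mixed model fitted to all infants would implicitly project an 18-month LAZ for those who died.

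All of this stands. What it leaves untouched is that the primary estimate rests on an unstated, untested assumption when a better-informed analysis is possible with data already scheduled.

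**Conclusion.** The concern holds as an improvement that should be made; it does not invalidate the plan. The 18-month LAZ analysis is complete-case by construction, omits the child's own earlier lengths, and has no missing-data sensitivity analysis. The possible bias is 0.05 to 0.15 SD (17% to 50% of the target effect) at 25% loss, if the gap between lost and retained children differs by 0.2 to 0.6 SD between arms. That differential is assumed, and the bias is zero if rates and gaps are equal. The precision gain is from 216 to about 227 to 247 effective children per group (power about 82% to 86% against 80%), again under assumed correlations and loss patterns.

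The point applies to 18-month LAZ only. Birth length, the other primary outcome, has no earlier length to draw on.

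**What to change.** Amend the SAP before unblinding; section 1.0 says it was written during data collection, before any results were known.

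1. Estimate the 18-month group effect from a likelihood-based repeated-measures model of LAZ at 0, 3, 6, 12 and 18 months: PROC MIXED, group by visit, unstructured covariance, the section 4.11 covariates. Multiple imputation of 18-month LAZ from earlier lengths is an acceptable alternative, but the sentence in section 3.2 would then need rewording.
2. Keep the PROC GLM ANCOVA as the complete-case analysis.
3. Add a delta-shift analysis that varies the assumed mean of lost children separately by arm. It is also needed for children with no length at all, whom earlier lengths cannot help.
4. State how infant deaths and pregnancy losses are handled; an 18-month LAZ should not be projected for them.

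The cost is SAP wording and modest programming, with no new data. The trade-off is reliance on loss being at random given earlier lengths, which is weaker than the present assumption but still untestable; hence item 3.

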3.3 Treatment groups

Study participants who completed baseline anthropometric and laboratory assessments were randomized into three groups using block randomization, to ensure even distribution of groups across time. Sealed, opaque envelopes bearing the group designations were prepared (by Study Statistician) and arranged in groups (Blocks), each block containing nine envelopes. There were 96 blocks in all, numbered block #1 to block #96, hence a total of 864 (96 x 9) envelopes. For each woman being randomized, the Study Nurse doing the randomization took the topmost 9 envelopes (i.e. starting with block #1), shuffled the nine envelopes in the block, and then offered the woman a choice of any of the nine. After woman made a pick, Nurse returned the remaining eight envelopes to the top of the pile. This process of presenting nine envelopes at a time for each woman to make a pick continued until there were less than nine envelopes left in the whole pile (block #96).

3.4 Data collection and follow-up

The variables on which we collected data, and the forms containing the variables are shown in Appendix A (for women) and Appendix B (for infants).

3.5 Interim data analysis

For each of the study outcome measures, we will not perform any interim analysis during the period primary data collection is ongoing. That is, for each outcome variable, analysis will be done only at the end of the data collection for that outcome. However the Data and Safety Monitoring Board (DSMB) and Institutional Review Board (IRB) can request interim analysis of

morbidity and all-cause mortality, by treatment group. In case of any evidence of a difference between treatment groups in morbidity and/ or all-cause mortality, DSMB will inform the Study Management Team and advise the appropriate course of action.

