1.0 Introduction

The International Lipid-based Nutrient Supplements (iLiNS) Project is a multi-country (Ghana, United States, Finland, France, Malawi and Burkina Faso) research collaboration with the goal to expand the evidence base for the use of lipid-based nutrient supplements (LNS) for preventing malnutrition in vulnerable populations. In Ghana the iLiNS Project focuses on the efficacy of LNS for pregnant and lactating women and their infants, and is referred to as iLiNS DYAD-G. Primary data collection began in December 2009. Below we describe the iLiNS DYAD-G's statistical analysis plan whilst data collection is still ongoing, before any knowledge of the study results. Data collection is expected to be completed by end of 2013.

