2.6 Blinding

The statistical analysis plan was written by study investigators, all of whom were blinded to the group assignments, until the final study results are released by the study statistician.

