2.7 Efficacy outcomes

2.7.1 Primary efficacy outcomes

The study has two primary efficacy outcomes, namely:

- a) Length of baby delivered by enrolled woman measured within 48 hours of delivery, which is defined by (i) Crude length in cm, and (b) Length-for-age z-score, and
- b) Length-for-age z-score of child at 18 mo of age.

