		- Parity	- Parity
		- Season at enrolment	- Season at enrolment

Covariates	Effect modifiers
- Mother's marital status	- Maternal anemia at enrollment
	- Mother's marital status

4.12 Selection of covariates and effect modifiers in the analysis of secondary outcomes Prior to analyses for secondary outcomes, this SAP will be updated with an *a priori* list of covariates and effect modifiers, as has been done for the primary outcomes above.

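### Secondary-outcome and repeated-measures plans fall due only before each later analysis, so they can be written after birth results by group are known

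*SAP*

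**What the plan says.** The SAP has two primary outcomes (2.7.1). The first is "Length of baby delivered by enrolled woman measured within 48 hours of delivery", and the second is "Length-for-age z-score of child at 18 mo of age".

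On timing, 3.5 begins with a general statement, "we will not perform any interim analysis during the period primary data collection is ongoing", and then explains it outcome by outcome: "for each outcome variable, analysis will be done only at the end of the data collection for that outcome".

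On what is still to be written:

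- Section 4.10 defers secondary outcomes at single time points not yet covered. On longitudinal data it says "Prior to analysis of repeated measures, this SAP will be updated to include the specific analyses and the presentation of the results".
- Section 4.12 says "Prior to analyses for secondary outcomes, this SAP will be updated with an" advance list of covariates and effect modifiers, as the primary outcomes already have.

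On blinding, 2.6 says that the investigators who wrote the plan were "blinded to the group assignments, until the final study results are released by the study statistician". Section 1.0 says that the plan is being described "before any knowledge of the study results", with data collection expected to finish by the end of 2013.

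**The concern.** A covariate or modifier list protects against selective modelling only if it is fixed before its authors know results that could guide the choice. Here the deadline for each list is the analysis it serves. It is not the first by-group result of any kind.

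The outcomes involved are not remote from one another. Section 2.7.2 lists child weight, length, head circumference and arm circumference at 3, 6, 12 and 18 months, motor milestones, and neuro-behavioural development at 18 months. All are measured in the children whose birth length is compared first, and later length is the same measurement repeated. Someone who knows whether birth length differed between groups, and which modifiers showed an interaction, could be guided by that when choosing modifiers for 3-, 6- and 12-month growth or the form of a growth model.

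What is at stake is the credibility of the secondary, subgroup and longitudinal findings. A critic could say that their lists were set in advance in name only, and as the plan stands the trial could not show otherwise.

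**Working it through.** The SAP gives no figure for this point, so the check is a comparison of clauses plus date arithmetic. The sample-size calculation in 3.1 plays no part in it.

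**Step 1: when birth data close.** Inputs: data collection expected to end by the end of 2013 (1.0); last primary measurement at 18 months of age (2.7.1). If the last 18-month visit falls in December 2013, the last birth falls 18 months earlier, in about June 2012. From then on, 3.5 permits a by-group analysis of birth outcomes.

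**Step 2: how much follow-up is then outstanding.** The SAP does not give the distribution of births, so this step rests on assumptions.

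- First enrolment is taken as December 2009, when primary data collection began (1.0), and pregnancy as 40 weeks.
- A woman enrolled at the 20-week limit delivers (40 − 20)/4.345 = 4.6 months later, in about April 2010.
- At the other extreme, (40 − 0)/4.345 = 9.2 months gives about September 2010.
- Births are taken as evenly spread from the first birth to June 2012, which is 26 months in the first case and 21 in the second.
- Share of children not yet at 18 months when birth data close: 18/26 = 69% to 18/21 = 86%.

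On these assumptions most of the 18-month data would still be uncollected when birth results could first be known.

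**Step 3: what is open and what is fixed at that point.**

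| Element | Status in the SAP |
|---|---|
| Covariates and modifiers for birth length and 18-month length-for-age | Listed in 4.11 |
| Testing sequence and 10% rule for keeping covariates | Fixed in 4.8 |
| Procedures (GLM, FREQ, LOGISTIC, MIXED, GLIMMIX) | Named in 4.10 |
| Several secondary outcomes at birth and 18 months, with tests | Laid out in Tables 2 to 4 |
| Covariate and modifier lists for secondary outcomes | Deferred by 4.12 |
| Additional single time points and their presentation | Deferred by 4.10 |
| Specific repeated-measures analyses | Deferred by 4.10 |

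The 10% rule in 4.8 selects from a candidate list, so it does not replace the missing list. Section 4.6 says that the modifiers for each analysis are given in later sections, but for secondary outcomes 4.12 postpones them.

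**Step 4: whether any clause ties the open items to the first result.** None does. Sections 4.10 and 4.12 each set the deadline as before the analysis concerned. Section 2.6 is the only other candidate, and it leaves two questions open. It does not define final results, and because 3.5 works by outcome, birth results could be read as final for that outcome. It also protects only knowledge of assignments. A birth comparison under coded labels would comply, yet would still show whether groups differ and which modifiers interact.

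**The case against.** The strongest reply is that 3.5 and 2.6 govern different things. Section 3.5 says when an analysis may be run, and 2.6 says when investigators learn the assignments. Both can be honoured if the study statistician analyses birth data and releases nothing until the end. On the more natural reading of 2.6, final results means the end of the whole trial. Much of the plan is also already fixed, and 2.7.2 and 4.7 give time points and measurement windows for most outcomes. These points stand, and they limit the concern to the deferred items.

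They do not close the gap. The natural reading of 2.6 is not the only one, and even on that reading results under coded groups are not covered.

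A reader might infer more than the text supports:

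- *That birth data will be analysed immediately.* Section 3.5 sets an earliest time. It permits an early analysis and does not schedule one.
- *That 3.5 contradicts 1.0 and 2.6.* Section 1.0 describes the present plan and promises nothing about later updates. Section 2.6 is ambiguous on this point, which is not the same as contradictory.
- *That the number of candidate modifiers in 4.6 measures the harm.* Testing many interactions raises the chance of a false positive whether the list was written early or late. That is a multiplicity matter and says nothing about timing.
- *That staff measuring children would be influenced.* Nothing in the SAP says that field staff receive by-group results.

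**Conclusion.** The point holds in a limited form. The plan permits the deferred secondary and repeated-measures choices to be written after by-group birth results are known, in a window of up to about 18 months before follow-up ends. Section 2.6 does not clearly prevent this. The primary analysis of 18-month length-for-age is not exposed, because its covariates and modifiers are already listed.

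The 18-month window follows from the two primary time points. The 69% to 86% of children still to reach 18 months rests on the assumed first-birth dates and an even spread of births. The effect on error rates cannot be quantified from the SAP, and no sample size, power or alpha figure changes. The conclusion does not assume that anyone intends an early look, only that the plan as written could not rule one out. It is worth acting on mainly because the remedy is cheap.

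**What to change.** - In 4.10 and 4.12, replace the analysis-by-analysis deadline with a single one. All updates (secondary covariate and effect-modifier lists, additional single time points, repeated-measures specifics) are to be completed and dated before the first by-group comparison of any outcome, under true or coded labels, is released to the investigators.
- In 2.6, define final study results consistently with that deadline, and say whether releasing birth results or coded-group results ends the blinding.

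The cost is SAP wording and writing the secondary sections sooner. Birth results need not be delayed. Withholding all by-group results until the 18-month data are locked would also close the gap, but it would hold back birth results by up to about 18 months. That is a trade-off for the sponsor and is not needed to resolve this point.
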